## 2.4 Sample Size

The sample size for cohort 1 was planned to be 12-24. This is based on a 6+6 design with dose de-escalation.

The sample size for cohort 2 was estimated as 36. The estimated ORR for treatment with the combination of tabelecleucel and pembrolizumab is  $\geq 45\%$ . The comparator ORR deemed uninteresting is 20%. Based on the exact binomial test at the 1-sided alpha = 0.025 significance level, a sample size of 36 subjects would provide 90% power to detect a true ORR of at least 45%.

## 3 STUDY ENDPOINTS

NPC disease response and progression were to be assessed via protocol-specific criteria by the study site per RECIST 1.1. Response-related endpoints assessed by investigators per iRECIST was planned to be used for supportive analyses.

### 3.1 Primary Endpoints

The primary endpoints are:

- The incidence of DLTs in Cohort 1

- The MTD, or in the absence of an MTD the RP2D, of tabelecleucel when administered in combination with pembrolizumab
- The ORR of tabelecleucel in combination with pembrolizumab
- The characterization of the safety profile of tabelecleucel in combination with pembrolizumab in subjects with NPC.

### **3.2 Secondary Endpoints**

- CR rate, DOR, PFS, and OS
- iRR (ie, iCR + iPR rate) and DOIR

As study terminated, not all endpoints will be analyzed in final CSR. Incidence of DLTs will be summarized as part of the safety section, efficacy summary will be limited to ORR only, Subject survival information will be provided by listing and swimmer plot.

## **4 ANALYSIS SETS AND SUBGROUPS**

### **4.1 Analysis Set**

Full Analysis Set consists of all subjects who have received at least 1 dose of IP (tabelecleucel or pembrolizumab). Safety Analysis Set will be identical to the full analysis set. All efficacy and safety analyses will use the Full Analysis Set.

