9 STATISTICS

9.1 Analysis Populations

The efficacy and safety populations will include all subjects enrolled in the study and who receive any investigational product. The efficacy population will be for the primary efficacy analyses, and all analyses of disposition, demographic and baseline disease characteristics.

In order for a subject to be considered evaluable for the analysis of DLT, the subject should have either had a DLT during the 21-day DLT assessment window or had completed the 21-day DLT assessment. Otherwise, a replacement subject will be added to Cohort 1.

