## **6 GENERAL PRINCIPLES**

### **6.1 General**

The Full Analysis Set will be used for all the safety analyses unless otherwise specified.

Unless otherwise specified, all continuous variables will be summarized using descriptive statistics, which will include the number of subjects with a valid measurement (n), mean,

standard deviation (SD), median, 25th percentile (Q1) and 75th percentile (Q3), and minimum and maximum. All categorical variables will be summarized using frequencies and percentages.

The following terms may be used for tables, figures and listings (TFLs):

- **Investigational product (IP):** Investigational product refers to tabelecleucel (Atara IP) or pembrolizumab (non-Atara IP) in this study.
- **Study treatment:** Study treatment refers to all the protocol-specified treatments administrated to subjects. In this combination therapy study, study treatment refers to tabelecleucel and/or pembrolizumab.
- **Enrolled subjects:** Enrolled subjects are those who signed informed consent and met the inclusion/exclusion criteria.
- **Enrollment date:** Enrollment date is the date the subject was enrolled
- **Study day:** Study Day 1 is defined as the day of the earlier of the first administration of tab-cel or pembro. Study day is defined as the date of interest minus Study Day 1 + 1 if the date is on or after the first dose date. If the date is before Study Day 1, study day is defined as the date of interest minus Study Day 1. There is no Study Day 0.
- **Baseline:** Baseline in general refers to Study Day 1. The baseline value of a parameter (eg, vital signs, laboratory tests and efficacy endpoints) is defined as the last value on or prior to the day of the first IP administration.
- **Duration of treatment:** The duration of IP treatment is defined for tabelecleucel and pembrolizumab separately as the date of the last dose of IP minus the date of the first dose of IP + 1.
- **Treatment exposure period:** The treatment exposure period is defined for tabelecleucel and pembrolizumab together as the time from Study Day 1 through 30 days after the last administration of IP.
- **Year:** A year consists of 365.25 days
- **Month:** A month consists of 365.25/12 days
- **Week:** A week consists of 365.25/52 days

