# 8 EFFICACY ANALYSES

The Full Analysis Set will be the primary analysis set for efficacy analyses.

Efficacy analyses will be conducted separately for subjects who are checkpoint inhibitor naïve or PD-1/PD-L1 failures. The disease assessments will be performed by the investigators.

The exact binomial 2-sided 95% CI will be provided for binary endpoints, ORR.

If any anti-NPC therapy other than specified in the protocol, is initiated, disease assessment data after the initiation date will be censored for the purpose of the efficacy analysis.

Subjects may have post-cycle 1 response of indeterminate response (IR). In the event that a subject with an IR assessment has discontinued the study and has not proceeded to a subsequent assessment (eg, subject is lost to follow up or dies), then the IR response will be considered as progressive disease. If a subject is still on study and has an IR assessment without a subsequent assessment, then the IR response will be considered as not evaluable (NE).

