### 8.1 Analysis of the Primary Endpoint

#### 8.1.1 Primary Analysis

The incidence of DLTs (defined in section 5.2.3 of the protocol) will be evaluated for phase 1B part of the study from the subjects in Cohort 1 (by dose level if applicable).

The primary endpoint is ORR (overall response rate), responder is defined as the proportion of subjects who achieved Best Overall Response (BOR) of CR or PR after administration of up to the first 2 tabelecleucel cell products, clinical benefit is defined as the proportion of subjects who achieved Best Overall Response (BOR) of CR or PR or SD after administration of up to the first 2 tabelecleucel cell products. If any new anti-NPC treatment, other than specified in the protocol,

is initiated, response data after the initiation date will not be considered for the definition of response. Disease assessment during the follow-up stage will not be considered for ORR or CBR definition.

The ORR and CBR (clinical benefit response) and their corresponding 95% CI will be reported.

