  - The above summaries will be repeated for TEAEs that are related or possibly related to study treatment pembrolizumab or tabelecleucel respectively.
- By SOC and PT, sorted by alphabetic order of SOC, then by descending order of PT total frequency
  - Subject incidence of all TEAEs
  - Subject incidence of serious TEAEs
- By PT, sorted by descending order of PT frequency and then by alphabetic order of PT.
  - Subject incidence of TEAEs
  - Subject incidence of serious TEAEs
  - Subject incidence of TEAEs leading to death
  - Subject incidence of TEAEs leading to pembrolizumab or tabelecleucel discontinuation
  - Subject incidence of treatment related TEAEs
  - Subject incidence of treatment related serious TEAEs

- Subject incidence of treatment related TEAEs leading to pembrolizumab or tabelecleucel discontinuation
- By preferred term and worst severity grade
  - Subject incidence of TEAEs
  - Subject incidence of serious TEAEs
  - Subject incidence of treatment related TEAEs
  - Subject incidence of treatment related serious TEAEs
- A summary table of identified and potential risks including TEAEs of special interest (TEAESIs) by PT sorted by risk category and PT in descending order of frequency within a risk category. The Risk categories for tabelecleucel include:
  - infusion-related reactions
  - transmission of infectious disease(s)
  - cytokine release syndrome
  - GvHD event
  - And additional risk of tumor flare.
- A summary table of TEAEs of special interest (TEAESIs) by PT sorted by PT in descending order of frequency for Pembrolizumab include:
  - Overdose- >1000 mg or >/= 5 times the indicated dose
  - Elevated liver values per Pembro label
- A summary table of TEAEs of dose limiting toxicity by PT in descending order of frequency.

The primary cause of all deaths will be summarized.

A listing of all deaths, serious TEAE, and TEAE leading to treatment or study discontinuation, or leading to death will be provided.

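### The SAP defines no DLT-evaluable set, so DLT incidence falls on the Full Analysis Set, although protocol 9.1 limits that analysis to evaluable subjects

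*SAP*

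**What the plan says.** **Protocol.** Section 9.1 (repeated in the synopsis) says that, to be "considered evaluable for the analysis of DLT, the subject should have either had a DLT during the 21-day DLT assessment window", or else must have completed that window. Anyone who did neither is to be replaced. Section 4.7 has the matching replacement rule. It also replaces a subject who stops because of a DLT tied to the first pembrolizumab infusion, before any tabelecleucel.

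**SAP, analysis sets.** Section 4.1 defines a single population: "Full Analysis Set consists of all subjects who have received at least 1 dose of IP (tabelecleucel or pembrolizumab"). The Safety Analysis Set is identical to it. The section then says "All efficacy and safety analyses will use the Full Analysis Set". Section 6.1 repeats this for safety with a proviso: "The Full Analysis Set will be used for all the safety analyses unless otherwise specified". Section 8 says "The Full Analysis Set will be the primary analysis set for efficacy analyses".

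**SAP, DLTs.** Section 3.1 lists the incidence of DLTs in Cohort 1 as a primary endpoint. After termination, section 3.2 keeps it: "Incidence of DLTs will be summarized as part of the safety section". Section 8.1.1 takes the definition of a DLT from protocol 5.2.3 and says that the incidence "will be evaluated for phase 1B part of the study from the subjects in Cohort 1". Section 11.1 plans "A summary table of TEAEs of dose limiting toxicity by PT in descending order of frequency" and names no denominator. The SAP refers nowhere to the evaluability rule in protocol 9.1.

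**The concern.** The SAP imports the protocol's definition of what counts as a DLT but not its definition of who counts in the analysis. A programmer who follows the SAP would divide by every treated subject, including any whom the protocol treats as non-evaluable.

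The direction is known. Under protocol 9.1 a non-evaluable subject has by definition had no DLT in the window. Such a subject adds to the denominator and nothing to the numerator, so a non-zero rate can only fall, which favours the product. At stake is the accuracy of a primary safety endpoint that the SAP retains for the final report.

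**Working it through.** **1. Which set applies to DLT incidence?**
- Read as a safety analysis (SAP 3.2), it takes the Full Analysis Set under 4.1 and 6.1.
- Read as part of section 8, where 8.1.1 sits, it takes the Full Analysis Set under 4.1 and 8.
- The proviso in 6.1 would help only if another set were specified. The reference in 8.1.1 to Cohort 1 subjects adds no evaluability condition, and SAP 4.3 describes Cohort 1 simply as those enrolled in phase 1B.

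Either reading ends at all treated Cohort 1 subjects.

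**2. The plan's own figures.** Neither document gives an expected DLT rate or a number of evaluable subjects. The nearest figures are the dose rule in protocol 3.5 (proceed with at most 3 of 12, de-escalate with 4 or more) and the MTD limit in 5.2.3 (below 33%). They agree on a denominator of 12: 3/12 = 25.0% is below 33%, and 4/12 = 33.3% is not.

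**3. Size of the dilution.** Inputs:
- 12 subjects enrolled (SAP 1).
- Assumption: all 12 were treated.
- Assumption: k of them are non-evaluable and unreplaced. The documents do not give k, so 0, 1 and 2 are shown.
- x = number of DLTs, also not given, shown from 0 to 3.

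Formulas: Full Analysis Set rate = x/12; protocol 9.1 rate = x/(12 − k).

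| DLTs (x) | k = 0: n = 12, equal to the Full Analysis Set | k = 1: n = 11 | k = 2: n = 10 |
|---|---|---|---|
| 0 | 0% | 0% | 0% |
| 1 | 8.3% | 9.1% | 10.0% |
| 2 | 16.7% | 18.2% | 20.0% |
| 3 | 25.0% | 27.3% | 30.0% |

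Relative understatement = 1 − (x/12) ÷ (x/(12 − k)) = k/12. That is 1/12 = 8.3% with one non-evaluable subject and 2/12 = 16.7% with two, whatever the non-zero x. The largest absolute gap in the table is 30.0 − 25.0 = 5.0 percentage points. With no DLT the rate is 0% on either set.

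**The case against.** **All 12 were probably evaluable.** Protocol 4.7 replaces Cohort 1 subjects who leave the window early without a DLT, until the required number have completed it. One dose level requires 12, and SAP 1 reports 12 enrolled. Had anyone been replaced, more than 12 would be expected. SAP 2.2 also says that the safety review took place after Cycle 1 Day 21 of the last Cohort 1 subject. This stands as the most natural reading, but no document states the number evaluable, and the SAP gives the report no line on which to state it.

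**Leaving without a DLT is a narrow route.** Protocol 5.2.3 already counts as a DLT any treatment-related toxicity that ends treatment in Cycle 1, and missing more than 25% of doses of either product because of related events. Mostly unrelated early exits remain. This stands too, and lowers the likelihood of an effect.

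**The SAP does not revoke the protocol, and readers could reconstruct evaluability.** Listings of adverse events, the DLT table and the disposition summary would help a careful reader. But the SAP states its own rule for the analysis population, so this is more than silence on a detail.

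**Stronger readings that a reader might infer, and that the documents do not support:**
- *A pembrolizumab-only DLT would inflate the rate on the Full Analysis Set.* Protocol 9.1 counts any subject with a DLT in the window and sets no tabelecleucel condition; 5.2.3 counts toxicity related to either product. Section 4.7 replaces such a subject but does not say that the DLT leaves the analysis. On 9.1 as written, the two denominators agree for that subject.
- *The interval would be too narrow.* SAP 8 and 8.1.1 plan confidence intervals for response rate and clinical benefit rate only, and none for DLT incidence.
- *The MTD finding could change.* With three DLTs it would take three unreplaced non-evaluable subjects to give 3/9 = 33.3%, contrary to the replacement rule. The safety review is past and Phase 2 will not run, so no dosing decision depends on it.

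**Conclusion.** The concern holds in a limited form. The SAP states a population for DLT incidence that differs from the one in protocol 9.1, and it is the wrong denominator whenever a treated subject is non-evaluable. Assuming 12 treated and one or two non-evaluable, a non-zero rate would be understated by 8.3% or 16.7% in relative terms, at most 5.0 points for up to three DLTs.

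The effect may be zero. The documents are consistent with all 12 being evaluable and do not say otherwise, so this is not evidence that any reported rate is wrong. The consequence is confined to the reported DLT rate in a descriptive report of a terminated study. It still merits correction because the endpoint is primary and the mismatch, where it bites, favours the product.

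**What to change.** - Add a DLT-evaluable set to SAP 4.1, exactly as in protocol 9.1: a DLT in the 21-day window, or the window completed.
- Make it the denominator for DLT incidence in 8.1.1 and for the DLT table in 11.1.
- Report how many of the 12 were evaluable.
- If any DLT came before the first tabelecleucel dose, in a subject replaced under protocol 4.7, identify it in a footnote. Do not exclude it by adding a tabelecleucel-dose condition, which 9.1 does not contain.

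The cost is one set definition, two denominator references, one count and possibly a footnote, with no new data. The only downside is a slightly smaller denominator if any subject proves non-evaluable. If all 12 were evaluable, the change confirms the rate.

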### **4.2 Subgroups**

Per data limitation, no subgroup analysis is planned for CSR.

### **4.3 Subject cohorts**

Cohort 1, subjects enrolled in phase 1B part is called Cohort1 with sub-cohort of checkpoint inhibitor naïve and sub-cohort of PD-1/PD-L1 failures (ie, refractory to or relapsed after PD-1/PD-L1 treatment).

## **5 INTERIM ANALYSIS AND EARLY STOPPING GUIDELINES**

No interim analysis is planned for this study.

## **6 GENERAL PRINCIPLES**

### **6.1 General**

The Full Analysis Set will be used for all the safety analyses unless otherwise specified.

Unless otherwise specified, all continuous variables will be summarized using descriptive statistics, which will include the number of subjects with a valid measurement (n), mean,

standard deviation (SD), median, 25th percentile (Q1) and 75th percentile (Q3), and minimum and maximum. All categorical variables will be summarized using frequencies and percentages.

The following terms may be used for tables, figures and listings (TFLs):

- **Investigational product (IP):** Investigational product refers to tabelecleucel (Atara IP) or pembrolizumab (non-Atara IP) in this study.
- **Study treatment:** Study treatment refers to all the protocol-specified treatments administrated to subjects. In this combination therapy study, study treatment refers to tabelecleucel and/or pembrolizumab.
- **Enrolled subjects:** Enrolled subjects are those who signed informed consent and met the inclusion/exclusion criteria.
- **Enrollment date:** Enrollment date is the date the subject was enrolled
- **Study day:** Study Day 1 is defined as the day of the earlier of the first administration of tab-cel or pembro. Study day is defined as the date of interest minus Study Day 1 + 1 if the date is on or after the first dose date. If the date is before Study Day 1, study day is defined as the date of interest minus Study Day 1. There is no Study Day 0.
- **Baseline:** Baseline in general refers to Study Day 1. The baseline value of a parameter (eg, vital signs, laboratory tests and efficacy endpoints) is defined as the last value on or prior to the day of the first IP administration.
- **Duration of treatment:** The duration of IP treatment is defined for tabelecleucel and pembrolizumab separately as the date of the last dose of IP minus the date of the first dose of IP + 1.
- **Treatment exposure period:** The treatment exposure period is defined for tabelecleucel and pembrolizumab together as the time from Study Day 1 through 30 days after the last administration of IP.
- **Year:** A year consists of 365.25 days
- **Month:** A month consists of 365.25/12 days
- **Week:** A week consists of 365.25/52 days

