5.2 Administration of Investigational Products

A treatment/consolidation cycle in the Treatment Phase of the study will last 3 weeks (21 days) and consist of 1 dose of pembrolizumab administered on Day 1 and 3 doses of tabelecleucel administered on Day 1, Day 8 (\pm 2), and Day 15 (\pm 2) of each cycle; pembrolizumab will be administered approximately 1 hour before tabelecleucel.

During the Maintenance Phase of the study, a maintenance cycle will last 84 days. Subjects will receive pembrolizumab on Day 1, Day 21 (\pm 2), Day 42 (\pm 2), and Day 63 (\pm 2) and tabelecleucel on Day 1 of each 84-day cycle; pembrolizumab will be administered approximately 1 hour before tabelecleucel.

Pembrolizumab: Pembrolizumab will be administered using IV infusion on Day 1 of the 21-day treatment/consolidation cycle after all procedures and assessments have been completed (except vital signs, which will be measured before and after all investigational product infusions).

Pembrolizumab will be administered as a dose of 200 mg (adults \geq 18 years of age) or 2 mg/kg (children 12 to $<$ 18 years of age) using a 30-minute IV infusion. Investigators should make every effort to target infusion timing to be as close to 30 minutes as possible. However, given the variability of infusion pumps from study site to site, a window between -5 minutes and +10 minutes is permitted, ie, infusion time is 30 minutes (-5 min/+10 min).

The Pharmacy Manual contains specific instructions for the preparation of the pembrolizumab infusion and administration of infusion solution.

Tabelecleucel: Tabelecleucel will be selected for each subject from the bank of available tabelecleucel cell products based on matching \geq 2 HLA alleles, at least one of which is a restricting HLA allele, shared between the tabelecleucel source material (donor) and the subject.

Tabelecleucel will be administered via a slow IV push over 5 to 10 minutes at a dose of 2×10^6 cells/kg body weight (the Cohort 1 de-escalation dose is 1.0×10^6 cells/kg) after all procedures and assessments have been completed (except vital signs, which will be measured before and after all investigational product infusions).

5.2.1 *Timing of Dose Administration*

On the study days in which both investigational products are administered (ie, Day 1 of treatment/consolidation cycles and Day 1 of maintenance cycles), tabelecleucel will be administered 1 hour (\pm 10 minutes) after the completion of pembrolizumab.

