6.3 Treatment/Consolidation Phase (21-day Cycles)

All subjects will receive 2 treatment cycles (21-day), and depending on their response to treatment, subjects may receive additional treatment and/or consolidation cycles (21-day), refer to Section [15.2](#). During treatment and consolidation cycles, subjects will receive tabelecleucel on Day 1, Day 8 (± 2), and Day 15 (± 2) and pembrolizumab on Day 1 and have a response assessment within 7 days after Cycle 2 Day 15 and every treatment/consolidation cycle thereafter.

6.3.1 Treatment/Consolidation: Day 1

- Physical examination including weight
- AEs

- Concomitant medications
- Hematology panel: CBC with platelet count and differential
- Abbreviated chemistry panel: serum creatinine, TBILI, ALT, AST, alkaline phosphatase, glucose (fasting) and tests of thyroid function (TSH, T3, and T4)
- **Cycle 1 and Cycle 2 only:** **CCI**
[REDACTED]
[REDACTED]
[REDACTED]
- **Cycle 2 and subsequent cycles:** **CCI**
[REDACTED]
- Investigational product infusions:
 - Pembrolizumab will be administered prior to tabelecleucel
 - Tabelecleucel will be administered 1 hour (\pm 10 minutes) after completion of the administration of pembrolizumab only if no infusion reactions related to pembrolizumab are observed/reported or in the case of such a reaction, the subject has recovered
- Vital signs (body temperature, BP, HR, and respiratory rates) at the following times:
 - immediately before the pembrolizumab infusion
 - within 10 minutes following the conclusion of the pembrolizumab infusion
 - immediately before the tabelecleucel infusion
 - within 10 minutes following the conclusion of the tabelecleucel infusion
 - 1 hour (\pm 10 minutes) after initiation of the tabelecleucel infusion
 - **Cycle 1 only:** 2 hours (\pm 10 minutes) after initiation of the tabelecleucel infusion
 - If the subject experiences symptoms/signs of an infusion reaction, follow-up may be longer, as clinically indicated.

6.3.2 *Treatment/Consolidation: Day 8 and Day 15*

- Physical examination including weight
- Concomitant medications
- AEs
- **CCI**
[REDACTED]
- **Cohort 1, checkpoint inhibitor (PD-1/PD-L1) failed subjects only, at least 1 day after Cycle 1 Day 8 and prior to Cycle 1 Day 15:** tumor/active site biopsy as described in Section 7.2 (central laboratory); hematology and coagulation panels must be performed prior to biopsy
- **Cohort 1, Day 15 only,** Hematology panel: CBC with platelet count and differential

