- **Cohort 1, Day 15 only**, Full chemistry panel: sodium, potassium, chloride, total carbon dioxide, BUN, creatinine, glucose (fasting), total calcium, albumin, total protein, serum creatinine, TBIL, ALT, AST, alkaline phosphatase, and tests of thyroid function (TSH, T3, and T4)
- **Cohort 2, at least 1 day after Cycle 1 Day 8 and prior to Cycle 1 Day 15 optional** tumor/active site biopsy as described in Section 7.2 (central laboratory); hematology and coagulation panels must be performed prior to biopsy
- **Cycle 1 and Cycle 2 Day 15 only:** CCI
[REDACTED]
[REDACTED]
[REDACTED]
- Investigational product infusion: tabelecleucel
- Vital signs (body temperature, BP, HR, and respiratory rates) at the following times:
 - immediately before the infusion
 - within 10 minutes following the conclusion of the infusion
 - 1 hour (\pm 10 minutes) after initiation of the infusion
 - If the subject experiences symptoms/signs of an infusion reaction, follow-up may be longer, as clinically indicated.

6.3.3 **Treatment/Consolidation, Observation: Days 16 to 21**

Between Days 16 to 21 of each cycle, the following *required* assessments/procedures will be performed:

- Concomitant medications
- AEs
- **Cycle 2 and subsequent cycles:** Radiographic assessments (MRI or CT with contrast) as described in Section 7.1

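### The SAP baseline rule has no pre-dose condition, so for vital signs it selects a post-dose Day 1 reading or no definite reading; only descriptive change columns are affected

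*SAP*

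**What the plan says.** SAP 6.1 states "Baseline in general refers to Study Day 1", and defines Study Day 1 as the day of the earlier first dose of either product. It then gives the value rule: the baseline value "is defined as the last value on or prior to the day of the first IP administration". Vital signs, laboratory tests and efficacy endpoints are named as examples. Nothing requires the value to precede the infusion.

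Protocol 5.2 has procedures and assessments finished before each product is given, with one exception: "except vital signs, which will be measured before and after all investigational product infusions". Protocol 6.3.1 sets out the Day 1 readings, starting with the one "immediately before the pembrolizumab infusion". In Cycle 1 they end with a reading 2 hours (± 10 minutes) after tabelecleucel is started. Footnote g of the schedule in Protocol 15.1 confirms that 2-hour reading.

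SAP 11.4 summarises vital signs as observed value, change from baseline and percent change from baseline, by scheduled time point, and lists all vital-sign data. It gives no baseline definition of its own.

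**The concern.** A baseline is meant to be the untreated reference. For most parameters the day-level wording does no harm, because the Day 1 assessment is complete before dosing. Vital signs are the exception: they are measured repeatedly on Day 1, mostly after exposure has begun. The rule therefore fails for one of the parameters it names.

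At stake is how the change columns read. If a shift in heart rate or blood pressure is still present at the last Day 1 reading, the literal rule sets that row to zero. It also displays the shift with opposite sign in the pre-dose row, if that row is tabulated, and carries the offset into later visits. This sits uneasily with SAP 11.1, which treats adverse events on the day of first dose as treatment-emergent.

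**Working it through.** The plan states no figure to reproduce here. The check applies the SAP rule to the protocol's schedule.

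**Step 1: the Cycle 1 Day 1 readings (Protocol 6.3.1).**

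| Reading | Scheduled time | Before any product? |
|---|---|---|
| 1 | just before pembrolizumab | yes |
| 2 | up to 10 minutes after pembrolizumab ends | no |
| 3 | just before tabelecleucel | no (pembrolizumab given) |
| 4 | up to 10 minutes after tabelecleucel ends | no |
| 5 | 1 hour ± 10 minutes after tabelecleucel starts | no |
| 6 | 2 hours ± 10 minutes after tabelecleucel starts (Cycle 1 only) | no |

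One reading of six precedes exposure and five follow the start of pembrolizumab.

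**Step 2: timing of the reading that the literal rule selects.** Inputs from Protocol 5.2 and 5.2.1: pembrolizumab infusion 30 minutes (25 to 40); gap from its end to tabelecleucel 60 minutes (50 to 70). Input from Protocol 6.3.1: 120 minutes (110 to 130) from the start of tabelecleucel to reading 6.

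- Nominal: 30 + 60 + 120 = 210 minutes after pembrolizumab starts.
- Earliest: 25 + 50 + 110 = 185 minutes.
- Latest: 40 + 70 + 130 = 240 minutes.

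If reading 6 is missing, reading 5 becomes the last value, at 25 + 50 + 50 = 125 to 40 + 70 + 70 = 180 minutes. Footnote g can be read as timing reading 5 from the end of the tabelecleucel push. The push is given "via a slow IV push over 5 to 10 minutes", so the window would then be 125 + 5 = 130 to 180 + 10 = 190 minutes. If follow-up is extended for an infusion reaction, the last value is later still. If tabelecleucel is not given that day, the last value still follows pembrolizumab.

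**Step 3: does other text restore a pre-dose baseline?**

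- The use of nominal visits (printed in the heading of SAP 6.5) does not separate readings within Day 1.
- The multiple-value rule in SAP 11.2.1 is for laboratory data, works on dose date and sets no pre-dose condition.
- If SAP 6.1 is applied by date only, all six readings share the date, so the rule picks none of them in particular.

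**Step 4: effect on the columns.** Let V1 be the pre-dose reading, V6 the last Day 1 reading, Vt any other reading, and d = V6 − V1.

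- Absolute change, literal rule: Vt − V6 = (Vt − V1) − d. The row for reading 6 is 0 for every subject, and the row for reading 1 is −d. At any visit the mean change moves by minus the mean of d over the subjects present.
- Percent change, literal rule: 100 × (Vt − V6) / V6, against 100 × (Vt − V1) / V1 from the pre-dose value. Numerator and denominator both change, so this is not a simple shift by −d.

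Illustration with assumed heart rates V1 = 80, V6 = 90 and a later visit at 85, so d = 10. From the pre-dose value, the change is 85 − 80 = +5, or 5/80 = +6.25%. From the literal baseline, it is 85 − 90 = −5, or −5/90 = −5.6%. These values show the mechanism only; the documents give no d.

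**Step 5: which other outputs use the rule.** Day 1 laboratory assessments are completed before infusion (Protocol 5.2), and screening imaging must precede the first dose (Protocol 7.1.2.1). Performance status is scheduled only at screening and end of treatment (Protocol 15.1). On schedule, none of these takes a post-dose baseline.

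**The case against.** The best reply is that this is an ambiguity which any programmer would resolve by convention. A change table whose 2-hour row is zero for everyone would look broken at first sight. SAP 6.5 says that analysis data sets will be prepared but gives no derivations, so what would be programmed is unknown. That much stands. A reader might infer that the vital-sign tables will certainly use a post-dose baseline, and the documents do not support that inference. The reply does not cure the text, however: one reading of the rule gives a post-dose value, the other gives no definite value, and neither gives the pre-dose reading.

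Two further objections stand. The timing in step 2 shows which reading is selected, not how far any summary moves. And rewriting the general rule for every parameter could do harm: the documents do not say whether laboratory collection times are captured. Without them, a strict time-of-dose rule might push same-day laboratory baselines back to screening.

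A reader might also infer that acute infusion effects would be hidden. That goes too far. Changes that resolve before the last Day 1 reading still show in the change columns. Observed values are tabulated, every reading is listed, and adverse events are reported separately.

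**Conclusion.** The point holds in a limited form. As written, SAP 6.1 does not yield a pre-dose baseline for vital signs: it yields the last Day 1 reading, nominally 210 minutes after first exposure, or an undetermined one.

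The consequence is confined to two of the three vital-sign statistics in SAP 11.4, change and percent change. Both are descriptive, in a study that SAP 1 says was closed in Phase 1B with 12 subjects. Observed values, listings, adverse events, dose-limiting toxicities, laboratory summaries and ORR do not depend on it. The size depends on d, which the documents do not give; if d is zero, nothing changes. Severity is low.

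The conclusion assumes that the six readings are taken as scheduled and that no derivation outside these documents already sets a pre-dose rule.

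**What to change.** Add one sentence to SAP 6.1 or 11.4, limited to vital signs:

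> For vital signs, baseline is the last non-missing value taken before the start of the first investigational product infusion, i.e. the Cycle 1 Day 1 reading "immediately before the pembrolizumab infusion", or the screening value if that reading is missing.

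Leave the day-level rule as it is for laboratory tests, where it already works.

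No new data are needed. Protocol 6.3.1 schedules the pre-pembrolizumab reading as its own time point, and Protocol 6.2 schedules screening vital signs. The downside is that a subject without the pre-dose reading is compared with a screening value up to 28 days old.
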